#### Logic model

The intervention is hypothesized to work through a number of mechanisms, described in the logic model below. The logic model is the same as the logic model we designed before the pilot trial, with the exception of one of the mechanisms, which was reformulated from increased help-seeking behaviour to increased self-understanding and use of self-management strategy. This change was informed by pilot qualitative findings.

#### **Control condition**

The control condition is the Business As Usual support that young people eligible for Your Choice would receive in absence of the study. BAU will vary between Local Authorities and range in terms of intensity and techniques practitioners use.

#### Incentives or restrictions for those in each group

There are no incentives or restrictions on the delivery of the Your Choice intervention among young people allocated to a trained team. Study participants will receive £10 voucher upon completion of the baseline young person questionnaire and £25 upon completion of the endline young person questionnaire.

#### Period when the intervention is being delivered

Delivery of Your Choice was expanded in three tranches. Delivery starts with the training of teams in CBT-informed tools and techniques, which took place during three periods:

- Home Office stage: The first training phase started in December 2021 and saw a small number of teams across 32 Local Authorities (LAs) in London trained in and deliver Your Choice. In 5 of these LAs, the trained team was randomly selected from two candidates (in all of the other 27 LAs, the trained teams were non-randomly selected).
- YEF (internal) pilot stage: Training was extended to additional teams during the spring
  of 2022, in preparation for the YEF pilot trial of Your Choice between August 2022 and
  March 2023. In the majority of (but not all) cases, the selection of treated and control
  teams was randomised within LA. In some LAs however such randomisation was not
  possible because they could not name two untrained teams to participate in the pilot.
- YEF efficacy stage: LAs in London have put forward 2 or more untrained teams for randomisation at this stage. The delivery of training to randomly selected teams amongst those will happened during the summer of 2023 in preparation for the efficacy trial.

Following the training of teams, the assignment of young people to treatment and control teams and the delivery of Your Choice has expanded accordingly, starting in January 2022 and will continue uninterruptedly but with increasing number of teams until the projected end of the efficacy trial, in December 2024.

#### How the intervention providers are assigned to groups

The treated and control groups are defined at the team level, based on whether or not a team was assigned to be trained in Your Choice. Once a team has been trained at any of the three training stages, it can only act as a treated team in subsequent phases. If a team acts as a control team in one stage, it can be re-randomised in the next stage and possibly become a treated team.

#### Impact evaluation

#### Research questions or study objectives

The research questions have been informed by the logic model and designed to reflect the complex set of relationships between the Your Choice intervention and the primary and

secondary outcomes, the mechanisms underlying these relationships and the importance of contextualising factors in determining the strength of these relationships. Some of the mechanisms will be explored via quantitative analysis and some will be explored via qualitative analysis. The data collection plan will allow us to explore some contextual factors and how these influence the change, but not all of them.

The research questions are as follows:

# 1. Can an intervention informed by CBT techniques and practices, and delivered by trained frontline practitioners, reduce conduct problems among young people most at risk of being affected by violence?

This is the main research question, focusing on the impact of Your Choice on the primary outcome – an indicator for scoring in the high and very high range in the conduct problems subscale from the Strengths and Difficulties Questionnaires (SDQ).

The SDQ conduct problems subscale is a measure of children's ability to behave in a socially acceptable manner, considerate of others. Scores in the abnormal range of this subscale are highly prevalent among the target population, as shown in the Your Choice Internal Pilot Report. They have also been related to aggressive behaviour and predisposition to rule breaking (Essau et al. 2012, Yao et al. 2008), and are likely an important predictor and precursor of disruptive and criminal behaviour (Spaan et al. 2023).

This combination of factors explains our choice of primary outcome. Specifically, we expect that successful violence reduction interventions are especially effective among individuals scoring in the abnormal range of the SDQ conduct problems subscale, and that conduct problems are at the forefront of the causal chain of effects that may ultimately see violence reduction result from the intervention. Focusing on the most relevant part of the scale seems most adequate for the purpose of detecting changes in predisposition to aggressive and violent behaviour. The alternative of considering the continuous conduct difficulties index runs into the risk of diluting effects by averaging over heterogeneous groups by conduct difficulties. Other scales in the SDQ, such as that measuring prosocial behaviour, though certainly relevant to provide a comprehensive characterisation of the effects Your Choice and to explore its potential mechanisms, are not as directly and closely related to the ultimate goal of violence reduction, and hence will be considered secondary outcomes.

Our primary outcome will be measured at endline in the participant's survey administered at week 20 after recruitment.

The null hypothesis we will be that there is no difference in this outcome between young people allocated to Your Choice and young people allocated to business as usual.

# 2. Is there a difference in offending behaviour between young people allocated to work with a team of practitioner trained in Your Choice in comparison to young people allocated to work with a team of practitioner delivering BAU support?

The outcome of interest is whether participants are ever arrested in the first 16 months after recruitment, as recorded in the PCN database. This is a key secondary outcome given that it directly relates to and informs on Your Choice's goal of reducing violence among young people at most risk. However, the low frequency of criminal activity will raise challenges in detecting impacts on this variable, and the time lag to obtaining crime data will necessarily delay the analysis. For these reasons, we consider the study of impacts on crime activity to be exploratory.

Two intermediate outcomes will also be studied: the self-assessed and practitioner-assessed level of risk, measured at endline as part of the young person and practitioner survey taken in week 20 after recruitment. These will provide and earlier indication of effects on self and practitioners' perceptions of likelihood of engaging in risky behaviour.

The null hypothesis we will be testing are: (i) that there is no difference in arrest probabilities between young people allocated to Your Choice and young people allocated to business as usual and (ii) that there is no difference in the self and practitioner assessments of the young person's likelihood to engage in risky behaviour, between young people allocated to Your Choice and young people allocated to business as usual.

- **3.** What are the mechanisms through which Your Choice works? Specifically, in comparison to young people allocated to BAU support, do young people allocated to work with a team of practitioners trained in Your Choice:
  - Gain higher wellbeing and emotional self-regulation? These outcomes will be measured as part of the endline young person survey completed in week 20 after recruitment, using the Warwick-Edinburgh Mental Wellbeing Scale, the internalising subscales of the SDQ, and the Self-regulation subscale from the Trait Emotional Intelligence Questionnaire Adolescent Short Form (TEIQUE-ASF).
  - Have stronger relationships with their practitioners, with their family and other sources of social support? The outcome of interest will be the Social Connectedness Scale – Revised (SCS-R), included in the endline young person questionnaire (taken 20 weeks after recruitment).
    - Have a more prosocial behaviour? The outcome of interest will be the SDQ prosocial behaviour scale, measured as part of the endline young person questionnaire in week 20 after recruitment.
  - Have a stronger prosocial identity? The outcome of interest will be the ProSocial Identity Scale, measured as part of the endline young person questionnaire

4. Do the impacts of being allocated to a team trained in Your Choice differ by gender, age, ethnicity, special education needs, level of risk assessed by the practitioner?

#### Design

The full study is composed of an internal pilot and an efficacy phase. The pilot started in August 2022, with teams randomly assigned to Your Choice training in December 2021 and later in the Spring 2022. Young people assigned to the treatment and control arms during the pilot period were provided with the exact same treatment conditions that are planned for the efficacy phase, which starts one year later in August 2023 with additional teams randomly assigned to training in the Spring and Summer of 2023. The assignment mechanism of young people to teams also follows the same rule across the two periods. The data collected for participants in both periods is also similar, and includes background data, needs presented, session data and baseline and endline surveys. In particular, all primary and secondary outcomes have been collected for participants during the pilot period, as will be for the efficacy trial and following the same procedures. The consistency in design across the two periods allows us to treat the pilot as internal. Details of the design can be found in Table 1 below.

Table 1: Trial design

Trial design, including number of arms		Two-arm, cluster randomised	
Unit of randomisation  Stratification variables  (if applicable)		Teams of youth practitioners	
		Local Authority	
	variable	Conduct problems	
Primary outcome	modeliro	An indicator for scoring in the high and very high range of the conduct problems subscale of the Strengths and Difficulties Questionnaires.  Measured as part of the endline young person survey, administered at week 20 after recruitment during a session with the practitioner.	

	variable(s)	Offending activity, mental wellbeing, emotional self-regulation, social connectedness, internalising behaviours, hyperactivity, self-reported and practitioner-reported perceptions of young person's safety, prosocial behaviour and prosocial identity.
Secondary outcome(s)	measure(s) (instrument, scale, source)	Criminal activity: recorded arrest in Police National Computers during the period of 16 months after recruitment.  Self-reported and practitioner-reported perceptions of young person's safety: Young person and practitioner versions of "Checkpoint. A safety scale for young people", which is an instrument to measure young people's perceptions of safety developed by the research team. Part of the endline young person questionnaire, administered at week 20 after recruitment.  Wellbeing: The Short Warwick–Edinburgh Mental Well-being Scale (SWEMWBS). Part of the endline young person questionnaire, which is administered at some point between weeks 14 and 20 after recruitment.  Emotional self-regulation: Trait Emotional Intelligence Questionnaire – Adolescent Short Form (TEIQUE-ASF) – Self regulation subscale. Part of the endline young person questionnaire, administered at week 20 after recruitment.  Social connectedness: Social Connectedness Scale – Revised (SCS-R). Part of the endline young person questionnaire, administered at week 20 after recruitment.  Internalising behaviours: emotional difficulties and
		peer difficulties subscales of the SDQ measured at baseline and endline as part of the participant's

		surveys administered following recruitment and at week 20 after recruitment respectively.
		Hyperactivity: hyperactivity subscale of the SDQ measured at baseline and endline as part of the participant's surveys administered following recruitment and at week 20 after recruitment respectively.
		Prosocial behaviours: Strength and Difficulties prosocial behaviour subscale measured at baseline and endline as part of the participant's surveys administered following recruitment and at week 20 after recruitment respectively.
		Prosocial identity: Pro-social Identity Scale (PIDS) measured at baseline and endline as part of the participant's surveys administered following recruitment and at week 20 after recruitment respectively.
	variable	Conduct problems
Baseline for primary outcome	measure (instrument, scale, source)	Indicator for scoring in the high or very high range of conduct problems scale from the Strengths and Difficulties Questionnaires.
		Measured as part of the baseline participant's survey, administered in week 1 after recruitment, before the start of Your Choice.
Baseline for secondary	variable	Social connectedness score, internalising behaviour, hyperactivity, prosocial behaviour and prosocial identity, self-reported and practitioner-reported perceptions of young person's safety,
outcomes	measure (instrument, scale, source)	Social connectedness: The Social Connectedness Scale – Revised (SCS-R), survey of young person following consent before Your Choice starts (in some cases, some form of BAU work/support will have

already been taking place). Measured as part of the baseline participant's survey, administered in week 1 after recruitment, before the start of Your Choice.

Internalising behaviours: emotional difficulties and peer difficulties subscales of the SDQ measured at baseline and endline as part of the participant's surveys administered following recruitment and at week 20 after recruitment respectively.

Hyperactivity: hyperactivity subscale of the SDQ measured at baseline and endline as part of the participant's surveys administered following recruitment and at week 20 after recruitment respectively.

*Prosocial behaviours*: Strength and Difficulties prosocial behaviour subscale measured at baseline and endline as part of the participant's surveys administered following recruitment and at week 20 after recruitment respectively.

Prosocial identity: Pro-social Identity Scale (PIDS) measured at baseline and endline as part of the participant's surveys administered following recruitment and at week 20 after recruitment respectively.

Self-reported and practitioner-reported perceptions of young person's safety: Young person and practitioner versions of "Checkpoint. A safety scale for young people", which is an instrument to measure young people's perceptions of safety developed by the research team. Measured as part of the baseline young person and practitioner surveys, administered at week 1 after recruitment.

#### Randomisation

Randomisation across the full study (internal pilot + efficacy)

Randomisation is **at the unit of teams of practitioners**. The rationale for this is that practitioners within the same team interact a lot with each other. Randomisation at the level of the practitioner would therefore create too much of a risk of cross-contamination.

Randomisation is **stratified at the LA level**. This model ensures that there will be trained and control teams in all participating LAs, a configuration that aligns well with the model of funding for delivery of the intervention.

Randomisation happened in three phases, that correspond to three batches of funding for programme delivery mentioned earlier: the Home Office phase (December 2021), the pilot phase (spring 2022) and the efficacy phase (summer 2023). The randomisation procedure was the same at all phases, to ensure continuity and in line with the internal nature of the pilot. Specifically, in an initial step LA put forward a list of so far untrained teams that they have available for delivering Your Choice. Among LAs that have two or more teams available for training, the evaluators randomly select teams for being trained and teams for being controls. The randomisation code is developed in STATA 16. The outcome of the randomisation is communicated to LAs by the evaluators, and the training of selected teams is implemented.

To check adherence to randomisation in the efficacy trial, we will require LAs to provide a list of practitioners in each of the teams involved in the study and to let us know if and when they have been trained ahead of start of delivery in the efficacy phase.

Practitioners will know whether they are part of a treated or control team and therefore cannot be blind to the experimental assignment. When recruiting young people, practitioners will know the young person's experimental condition. This means that the young person may not be blind to the assignment at the time of recruitment. Training of practitioners and SPOCs around recruitment will strongly emphasize the need to recruit young people into the study (as opposed to an experimental arm) and to not divulge their treatment condition.

#### **Participants**

#### **Participating Local Authorities**

Teams involved in the full evaluation (across internal pilot and efficacy) are from 29 LAs. 28 of these 29 LAs will be involved in the efficacy phase of the trial. Among the 4 LAs of London that are not participating in the efficacy phase of the trial:

- One (Enfield) recruited into a randomised team during the pilot but is not able to participate in the efficacy trial
- Three (Lambeth, Wandsworth, Camden) were involved in the pilot trial but either did not recruit anyone, did not have teams to randomise or did not adhere to the randomisation in the pilot trial so as to be included in the internal pilot. These three

LAs also were not able to put forward teams to be randomised in the efficacy trial. Therefore, they are not represented in either the internal pilot or the efficacy trial.

Although these LAs must be excluded from the experimental evaluation of Your Choice given that they would jeopardise the experimental design, data will be collected on young people in these LAs assigned to trained teams delivering Your Choice, and to control teams. That data will be used to expand the sample size for a parallel non-experimental evaluation providing further support to the experimental results, and to further characterise heterogeneity in delivering Your Choice in practice by taking into account the diversity of LA environments.

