#### Rationale for planned number of participants

The planned number of participants in the efficacy phase is 1,857. This number includes:

- 179 young people recruited in randomised teams during the pilot phase (among them, 83 young people have endline young people questionnaires completed at the time of writing).
- 1,678 young people expected to be recruited in randomised teams during the efficacy phase (Aug 2023 – December 2024).

We believe the expected number of participants during the efficacy phase is realistic for the following reasons. First, these numbers have been discussed by the evaluation team in one-to-one conversations or email with each LA. Second, several LAs have purposely provided lower bounds to the numbers they think they can actually recruit in order to be realistic and successful in meeting these numbers. Third, the efficacy trial is planned to involve about five times as many randomised teams as the pilot trial did, and to last roughly 3 to 4 times as long as the pilot trial. We therefore think that it is reasonable for the number of participants in the efficacy trial to be at least 10 times higher than the pilot trial, or around at least 1,600 young people.

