#### **Analysis**

Our primary analysis uses only randomised teams during the Home Office, pilot and efficacy phases. It will involve various steps.

Step 1. Thorough check that the group of young people assigned to Your Choice appear to come from the same population as those assigned to the control group along many observed variables describing demographic characteristics (e.g. gender, age, ethnicity, etc), main activity at baseline (education or training, employment, other), whether looked after, special education needs, primary needs for Local Authority support (e.g. abuse, disability, family acute stress, etc), various measures observed in the baseline youth survey including SDQ scores and self-reported risk assessment, practitioner risk assessment from baseline practitioner questionnaire. We will also check that the distribution of services to which young people have been assigned look balanced across experimental arms. All subsequent analysis addressing the key research questions set out earlier in this document must rely on a good understanding of the comparability between the treated and control groups.

Step 2. Thorough check of the delivery of Your Choice in contrast with BAU, revealing the extent to which the programme effectively changes interactions between the youth workers and young people and characterising the intensity of treatment for different groups. Specifically, we will check that young people assigned to Your Choice received an intensive schedule of meetings with content that is specific to the programme (hence matching the Your Choice protocol), while young people assigned to the control teams did not. Again, all subsequent analysis and interpretation of findings must rely on a good understanding of what the programme delivers in comparison with BAU.

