# The London Young People Study: An evaluation of the Your Choice intervention Statistical analysis plan

Evaluating institution: Institute for Fiscal Studies and Anna Freud Centre Principal investigator(s): [name]

Project title 	The London Young People Study: Evaluation of the Your Choice Programme Using a Cluster Randomised Controlled Trial	
Developer (Institution)	London Innovation and Improvement Alliance (LIIA) Violence Reduction Unit (VRU)	
Evaluator (led)	Institute for Fiscal Studies	
Principal investigator(s)	[name]	
Protocol author(s)	[name], [name], [name], [name]	
Trial design	Two-armed cluster randomised controlled trial with random allocation at the youth practitioner level	
Trial type	Efficacy	
Evaluation setting	30 Local Authorities of London	

<sup>1 Please make sure the title matches that in the header and that it is identified as a randomised trial as per the CONSORT requirements (CONSORT 1a).

Target group	Any child aged between 11-18 years old who is assessed as medium or high risk of harm / vulnerability as a result of extra- familial harm and has been considered by a multi-agency panel (typically MACE / Pre-MACE)		
	The number of participants was initially estimated to be between 1700 and 1800 young people across the internal pilot and efficacy stage. Across teams that have ever been randomised, this included an expected 1698 young people recruited between August 2023 and December 2024 and 161 young people who were recruited during the internal pilot phase (82 of which we have endline data for). We expect a 70% data completion rate, which sets the overall sample for impact evaluation at 1,272.		

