#### Analysis

All codes and data needed to replicate the results from the efficacy trial will be provided. In preparing these replication materials, we will follow standard guidelines set out by the American Economic Association (American Economic Association (aeaweb.org).

The level of analysis for the core analysis will be the individual young person. The parameter that we will estimate in our main analysis with be an Intention-to-Treat (ITT) treatment effect measuring the effect on a young person's primary and secondary outcomes of being supported with a team that has trained in Your Choice (as opposed to a team that has not trained in Your Choice). The main Intention-to-Treat (ITT) specification related to our primary and secondary outcomes will be a linear regression, where we will control for baseline values of the outcome and baseline characteristics of the young person and/or their team that present statistically significant imbalances at baseline. In line with De Chaisemartin and Ramirez-Cueller (2022), we will present specifications with and without strata fixed effects. Some of the secondary analysis will be at the level of the meetings of the young-person and practitioner, and we will also consider some outcomes at the practitioner level – such as their assessment of the young person's needs and risks.

All methods were determined a priori and given what we have learned during the pilot phase.

We will use STATA version 16 or higher for the analysis.

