#### Primary outcome analysis

We will estimate the Intention-to-Treat (ITT) effect by estimating the following equation for young person i will be of the form:

$$Y_{i1} = \beta_0 + \beta_1 D_i + \beta_2 X_i + \beta_3 Y_{i0} + strata fixed effects + u_i$$

where  $Y_{i1}$  is the primary outcome of interest, which is an indicator that takes the value 1 if the young person scores in the high to very high conduct problems range and 0 otherwise, and  $Y_{i0}$  is the baseline value for that same outcome,  $D_i$  is an indicator for treatment assignment,  $X_i$  are any baseline characteristics of the young person and/or their team for which we find statistically significant imbalances between treated and control groups, and  $u_i$ is an error term. Standard errors will be clustered at the Local Authority level, following Chaisemartin and Ramirez-Cuellar (2022).

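### The protocol allows a Local Authority to be dropped for not adhering to its draw, and the SAP's prose states the ITT effect by training received although its model uses assignment

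*Protocol*

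**What the plan says.** **Exclusion.** Protocol, Participating Local Authorities, says of the study as a whole: "Teams involved in the full evaluation (across internal pilot and efficacy) are from 29 LAs". Three further LAs took part in the pilot but are in neither the internal pilot nor the efficacy trial, because they "either did not recruit anyone, did not have teams to randomise or did not adhere to the randomisation in the pilot trial". The last of these reasons reads in full that they "did not adhere to the randomisation in the pilot trial so as to be included in the internal pilot". The reasons are joined by *or* and are not attributed to individual LAs. The same section says that these LAs put no teams forward for the efficacy draw, and that their data will be collected for a separate non-experimental analysis.

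**Analysis set.** Protocol, Analysis: "Our primary analysis uses only randomised teams during the Home Office, pilot and efficacy phases". No adherence condition is attached. The summary tables of both documents likewise count participants across teams that were ever randomised.

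**The ITT effect.** SAP, Analysis, describes it as the effect of "being supported with a team that has trained in Your Choice (as opposed to a team that has not trained in Your Choice". SAP, Primary outcome analysis, says that the treatment variable in the regression "is an indicator for treatment assignment". The secondary-outcome model and the simple model under Robustness checks also use assignment. Protocol, How the intervention providers are assigned to groups, defines the arms by whether a team was assigned to training.

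**Non-compliance.** SAP, Compliance, accepts that non-compliance may make the ITT estimate understate the effect among those who received the programme. It estimates the effect of receipt by two-stage least squares, with allocation as the instrument.

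**The concern.** Two of the three exclusion reasons are sound: an LA with no recruits contributes no data, and an LA with no teams to draw was never randomised. The third is different. A team drawn by the evaluators stays randomised whether or not its LA trains it. Dropping the LA because it did not follow the draw conditions the analysis on behaviour after randomisation. LAs that swap or refuse a draw may do so for reasons tied to their teams and caseloads. The estimate then describes LAs that adhered and will probably exceed the effect across all randomised LAs. The instrumental-variable analysis also needs non-adherent units in the data, in their assigned arm.

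The wording of the ITT effect matters for the same reason. If an LA trains the wrong team, a rule based on training and a rule based on assignment put the same young people in opposite arms. This could happen: Protocol Table 9 rates wrong-team implementation as Medium for both likelihood and impact, and Protocol, Learnings from the pilot trial, reports good adherence in most cases, not all. Whoever coded treatment from the SAP's prose rather than from its equation would produce an as-treated comparison labelled ITT.

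**Working it through.** **1. LA count.** 28 efficacy LAs + 1 pilot-only LA = 29, which reproduces the protocol's figure. 28 + 4 not in efficacy = 32, and 32 − 29 = 3 left out. Let *k* be the number of these that were drawn and non-adherent. The documents do not give *k*, so it ranges from 0 to 3.

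**2. Effect of restoring them, each LA weighted equally (assumption).** Share *w* = *k*/(29 + *k*). The ITT effect is multiplied by (1 − *w*) + *w·c*, with *c* = 0 if those LAs had no treatment contrast and *c* = −1 if their arms were fully swapped. The last two columns apply the factor to the SAP's two minimum detectable effects, used here only as a scale.

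| *k* | *w* | *c* | Factor | 24% becomes | 22% becomes |
|---|---|---|---|---|---|
| 0 | 0 | either | 1.000 | 24.0% | 22.0% |
| 1 | 0.033 | 0 | 0.967 | 23.2% | 21.3% |
| 1 | 0.033 | −1 | 0.933 | 22.4% | 20.5% |
| 3 | 0.094 | 0 | 0.906 | 21.8% | 19.9% |
| 3 | 0.094 | −1 | 0.812 | 19.5% | 17.9% |

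With *k* = 3, leaving these LAs out overstates the all-randomised effect by 1/0.906 = 1.10 times (no contrast) or 1/0.812 = 1.23 times (full swap).

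**3. Weighting by participants.** Equal weights are too heavy, because these LAs could add pilot data only. Protocol Table 2 places pilot-recruiting teams in 5 LAs (pilot only) and 18 LAs (both phases). The overlap is not stated, so the total is between 18 and 23. The protocol reports 83 pilot participants with endline data.

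- Per LA: 83/23 = 3.6 to 83/18 = 4.6.
- Three LAs at average yield (assumption): 10.8 to 13.8 young people.
- Share of the analysed sample: 10.8/(1,272 + 10.8) = 0.84% with the initial target of 1,272, to 13.8/(1,094 + 13.8) = 1.25% with the revised 1,094.
- Full swap at the upper share: 1 − 2 × 0.0125 = 0.975, so 24% becomes 23.4%.

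**4. Statements on the ITT effect.** The arm definition, the primary model, the secondary model and the simple robustness model all use assignment. The use of allocation as instrument for receipt fits this. One sentence in SAP, Analysis, uses training received. The weight of the text is with assignment, and that sentence is the outlier.

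**The case against.** The strongest reply is that the estimate is by assignment, because the equation governs the analysis and its treatment variable is assignment. That stands. A reader might infer from the SAP's prose that the planned estimate is not by assignment at all. The documents do not support that: one loosely worded sentence does not override the model, the arm definition and the separate analysis of receipt. It is a contradiction to remove.

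A second reply is that randomisation is stratified by LA and the primary model has LA fixed effects, so dropping a whole LA removes both arms of that stratum and leaves the comparisons in the other LAs intact. This also largely stands. The main consequence is a narrower population. The protection is complete only if adherence did not depend on which team was drawn, and the documents do not say.

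Third, no LA is shown to have been dropped for non-adherence, since the reasons are alternatives. That is correct, and it is why the size below starts at zero.

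Two further inferences should be resisted. One is that efficacy LAs that train the wrong team will also be dropped. No section says so, and Table 9 answers that risk with communication and check-ins. What is missing is an explicit rule for analysing such teams. The other is that the fall in pilot numbers reflects adherence exclusions. The protocol counts "179 young people recruited in randomised teams during the pilot phase", 83 of them with endline data; the SAP counts "161 young people who were recruited during the internal pilot phase (82 of which we have endline data for". Nothing links the difference of 18 to adherence. Only one of the 18 had endline data (83 − 82), and the main estimates impute no outcomes. This is a separate reconciliation query.

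**Conclusion.** Two faults stand. Non-adherence to the draw is a stated ground for excluding an LA, and it conflicts with the plan's own analysis set and with its handling of non-compliance. The SAP's prose statement of the ITT effect contradicts its model and would give an as-treated comparison if followed.

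The effect on the headline estimate is probably small. It concerns zero to three LAs and pilot data only. At average pilot yield, three LAs would be about 0.8% to 1.3% of the analysed sample, and even fully swapped arms would move a 24% effect only to about 23.4%. The equal-weight figures, with overstatement of up to 1.10 or 1.23 times, are a generous upper illustration. Both rest on assumed weights and on assumed contrasts in the excluded LAs, since the documents give no counts for them. If none of the three was drawn, non-adherent and recruiting, the exclusion changes nothing and only the wording needs correction.

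**What to change.** 1. **SAP, Analysis.** State the ITT effect as that of being assigned to a team randomised to be trained, with treatment coded from the evaluators' randomisation file.
2. **Protocol, Participating Local Authorities, and the analysis-set definition.** Limit exclusion to LAs with no random draw or no recruits. Analyse every randomised team that recruited, in all phases, whether or not the LA trained it, in the arm of its most recent draw at the time the young person was recruited. The timing clause is needed because 8 pilot control teams were validly redrawn to treatment for efficacy. They count as control in the pilot and treated in efficacy. This sentence also supplies the missing rule for efficacy teams that depart from their draw.
3. **Disclosure.** Say which reason applied to each of the three LAs and, for any that was drawn and non-adherent, give team and participant counts. Restore any with outcome data to the primary ITT analysis, and leave non-adherence to the planned complier average causal effect analysis.

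The cost is a few sentences in the two documents and the recoding of at most a few pilot records. The protocol already plans to collect data from these LAs. The statistical price is slight dilution of the ITT estimate.
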